5.0 STUDY PROCEDURES

Table 7: Study Visit Parameters

	Baseline (-28days)	On Treatment								Off Treatment	Follow-Up ⁱ	
	Screening ^j	Cycle 1 ^{l, n}				Cycle 2 ^{g, l, n}				Cycle 3+ g, l, n	End of study treatment	
Week	0	1	2	3	4	5	6	7	8	9+		
Regorafenib 160 mg ^e		On			Off	On			Off	Continue ^e		
Informed consent	X											
Medical history ^h	X											
Physical examination	X	X				X				X	X	
Vital signs ^a	X	X	X	X	X	X	X	X	X	X	X	
CBC/Diff	X	X				X				X	X	
PT/INR ^b	X	X ^b				X ^b				X ^b	X ^b	
Clinical chemistry ^c	X	X		X		X		X		X ^c	X	
Pregnancy test ^f	X											
Urine Protein/Creatinine Ratio (UPC)	X											
ECOG PS	X	X				X				X	X	
Disease Measurements ^d	X ^d									X ^d	X ^d	
Study medication dispensing & pill diary collection		X				X				X		
Tolerability/AE reporting	X	X	X	X	X	X				X	X	
Adverse Event Self- Report Survey (AESRS)		X ^k				X				X		
Concomitant medications	X	X				X				X	X	
Phone call ^{m, i}			X ^m	X ^m	X ^m							X ⁱ

- a- Vital signs to include height (height is recorded at screen visit only), weight, blood pressure, pulse, temperature. **Blood pressure should be monitored weekly for the first six weeks of study treatment. A patient blood pressure log will be maintained to aid in monitoring (See Appendices). Patients will record blood pressure at home during the weeks they are not coming to the clinic for exams.**
- b- PT/INR should be closely monitored on day 1 of each cycle.
- c- Electrolytes, calcium, magnesium, BUN, serum creatinine, total bilirubin, AST, ALT, alk phos, albumin, amylase, lipase. Should be done every 2 weeks during Cycles 1 and 2; if no abnormalities are seen, may be done on day 1 only of subsequent cycles. Mid-cycle labs may be performed at a local laboratory if needed to accommodate patient travel logistics..
- d **Imaging should be done as clinically indicated** (i.e. CT, MRI and visual measurements), which satisfy RECIST v 1.1 to evaluate disease (such as in extremity, head and neck). Imaging studies will be done at baseline (within 4 weeks (28 days) before the first dose) and repeated after every 2 cycles of treatment (prior to each odd cycle) for tumor response evaluation.
- ePatients will receive regorafenib daily x 3 weeks followed by 1 week off (1 cycle = 4 weeks).
- f- Women of child-bearing potential must have a negative serum pregnancy test within 7 days prior to registration.

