- g- Assessments including physical examination, vital signs, ECOG PS, clinical chemistry, CBC/Diff and PT/INR should immediately precede initiation of the next cycle of therapy. Clinically indicated scans should be performed during the off week immediately preceding initiation of odd numbered cycles.
- h- Medical history findings (i.e. previous diagnoses, diseases or surgeries) will be collected, including those not pertaining to the study indication, beginning before registration, that are considered relevant to the study.
- i- Once off treatment, patients will be followed approximately every 6 months by phone for survival endpoints. Follow-up will continue up to 5 years.
- j- Screening assessments must be completed within 15 days prior to registration, unless otherwise specified. Screening assessments may be used for C1D1 assessments if completed \leq 15 days before study drug initiation.
- k- Adverse Event Self-Report Survey (AESRS) should be disseminated to each patient on day 1 of cycle 1, but no data is collected.
- l- Unless otherwise noted, on-therapy windows for testing will be as follows: imaging scans should be completed within +/- 1 week of the target time point, and labs and physical examination within +/- 3 days of the target time point .
- m- Subjects will be instructed to follow-up weekly with the study team IF they are experiencing any side effects.
- n- Day 1 of each cycle should be every 28 days. In the event that this day falls on a holiday or other such event, study team should use +/- 3 day window to complete pre-treatment procedures, and dispense protocol agents to patients with instructions to commence treatment on day 1. Any missed doses will not be made up and should be skipped to maintain a 28-day cycle.

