6.3 SECONDARY ENDPOINT ASSESSMENT

The progression-free rate (PFR) at 3 and 6 months will be defined as the number of patients with progression absent at these timepoints divided by the total number of study patients. Median PFS (defined as the duration of time from start of treatment until time of progression or death, whichever occurs first) will be estimated as a secondary endpoint. Overall survival will be defined as the time from start of treatment until death by any cause. Response rate (by RECIST v 1.1) will be calculated using the definitions above. The rate and duration of tumor control will be defined as the number of CR+PR+SD responses. Patients must complete at least 2 cycles of study treatment to be considered evaluable for efficacy endpoints.

To evaluate the safety and tolerability of regorafenib, all subjects who receive at least one dose of study treatment will be considered evaluable for the safety analysis. Safety variables will include the following: AEs, laboratory changes (complete blood counts, electrolytes, chemistry, and coagulation), changes in vital signs (blood pressure, heart rate, respiratory rate, and temperature) and results of clinically indicated studies outside study guidance, such as ECG or chest x-ray images, as produced at the investigator’s discretion. All AEs whether considered drug-related or not, will be reported with a diagnosis, start/stop dates, action taken, whether treatment

was discontinued, any corrective measures taken, outcome, and other possible causes. For all events, the relationship to treatment and the intensity of the event will be determined by the investigator. All observations pertinent to the safety of the study treatment will be recorded and included in the final report. This trial will use the NCI CTCAE v 4.0 criteria for assessment of toxicity and SAE reporting with regard to toxicity grade.

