7.3 ADVERSE EVENT REPORTING

7.3.1 Routine Reporting

All routine adverse events, such as those that are expected, or are unlikely or definitely not related to study participation, are to be reported on the appropriate eCRF according to the time intervals noted in the Schedule of Events. Routine AEs will be reviewed by the Data Monitoring Committee (DMC) according to the study's phase and risk level, as outlined in the DSMP.

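### Table 7 marks AE reporting for everyone in cycle 1 weeks 2 to 4, but footnote m leaves the phone call in those weeks to the patient, which risks incomplete recording of transient early symptoms

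*Combined protocol and SAP*

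**What the plan says.** In Table 7 (Section 5.0) the row "Tolerability/AE reporting" is marked in each of weeks 1 to 4 of cycle 1, and no footnote qualifies those marks. Section 7.3.1 says that routine AEs "are to be reported on the appropriate eCRF according to the time intervals noted in the Schedule of Events". Section 6.3 adds: "All AEs whether considered drug-related or not, will be reported", with start and stop dates among the details. Safety and tolerability is a secondary objective (2.2.6), and Section 9.4 tabulates AEs by grade and frequency.

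The phone-call row of Table 7 is marked in weeks 2, 3 and 4 only, each time with footnote m: "Subjects will be instructed to follow-up weekly with the study team IF they are experiencing any side effects".

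Three other provisions bear on those weeks:

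- Footnote c, on chemistry: "Should be done every 2 weeks during Cycles 1 and 2". In cycle 1 this falls in weeks 1 and 3. A local laboratory may do the mid-cycle draw.
- Section 4.3.3 has blood pressure taken at the study site at least weekly for six weeks, whereas footnote a says: "Patients will record blood pressure at home during the weeks they are not coming to the clinic for exams".
- Footnote k says that the self-report survey "should be disseminated to each patient on day 1 of cycle 1, but no data is collected".

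**The concern.** The AE row and the phone row describe the same three weeks in different ways. The AE row expects an entry for every patient. Footnote m turns the contact marked for those weeks into one that the patient starts, and only after deciding that there is something to report.

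These weeks hold three of the four cycle 1 AE entries. If week 1 is the day 1 visit, as footnotes k and n suggest, they are the only cycle 1 AE entries after dosing has begun. The next AE assessment, in week 5, comes after the week off drug, when a short-lived symptom may have eased. At stake is how complete the early record of symptomatic events is, with their onset dates and peak grades. The hand-foot skin reaction rules in Section 4.3.2 also count occurrences and look at improvement within seven days, so they rely on dated detection.

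**Working it through.** The plan states no figure for AE ascertainment, so there is none to reproduce. The check is a reading of Table 7 by week.

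| Table 7 row | Wk 1 | Wk 2 | Wk 3 | Wk 4 | Wk 5 |
|---|---|---|---|---|---|
| AE reporting | X | X | X | X | X |
| Phone call | – | X (m) | X (m) | X (m) | – |
| Physical examination, ECOG, concomitant medications | X | – | – | – | X |
| Vital signs | X | X | X | X | X |
| Chemistry | X | – | X | – | X |
| Self-report survey | X (k) | – | – | – | X |

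**Two readings.** If the AE row governs, staff must obtain AE status from every patient in weeks 2 to 4. If footnote m governs, an entry arises only when a patient calls. Under the second reading, a blank entry could mean asked and none, not asked, or did not call. The text does not say which reading applies.

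**What does not depend on the call.**

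- Blood pressure is collected weekly, at the site or at home.
- Chemistry is collected in week 3.
- SAEs are reported within 24 hours of awareness (7.3.4.1).
- Week 5 has an unconditional AE assessment with physical examination, and Section 7.3.3 requires start and stop dates, so earlier events can be entered then.

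**What remains.** Non-serious symptoms that start and settle within weeks 2 to 4, or whose onset and worst grade are poorly recalled at week 5.

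**Size.** Recorded patients = N × p × c, where p is the true proportion with an event and c the proportion captured. The documents give no c. For arithmetic only, take N = 31 and p = 0.17 or 0.561, the hand-foot skin reaction rates quoted in Section 1.3.2. Those are rates of grade 3 or worse in other diseases, so they are not rates of the mild, transient events at issue.

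| Assumed c | p = 0.17 | p = 0.561 |
|---|---|---|
| 1.0 | 5.3 | 17.4 |
| 0.9 | 4.7 | 15.7 |
| 0.7 | 3.7 | 12.2 |
| 0.5 | 2.6 | 8.7 |

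If week 5 recall were complete (c = 1), nothing would be lost.

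**Number of calls.** Three per patient: 3 × 12 = 36 if the trial stops after stage 1, and 3 × 31 = 93 if it reaches 31 patients. The Section 9.3 early-termination probability reproduces: P(X ≤ 3) for n = 12 and P = 0.22 is 0.739, with average N 16.96. Expected calls at P = 0.22 are therefore 3 × 16.96 = 50.9.

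**The case against.** The strongest reply is that this is a small clarification.

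- Footnote m sits on the phone row, not the AE row, so a site could comply with both.
- Section 7.3.1 governs when AEs are reported, not how they are elicited, and Section 10.5 generally makes data due at the end of each cycle, within 10 days.
- Any side effect is a low threshold for calling.
- Table 7 has no AE entry in weeks 6 to 8, so the plan already accepts capture at the next visit.
- The AE analysis is descriptive, in a single-arm trial.

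Most of this stands and limits the loss to transient, non-serious symptoms. It does not settle who must obtain the week 2 to 4 entry that Table 7 marks for everyone.

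Several stronger readings are tempting but not supported:

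- A reader might infer that early toxicity is in fact recorded differently by site and under-recorded. Footnote m is one instruction to all six sites. Site differences arise only if sites resolve the conflict differently, and the documents contain no data on that.
- A reader might infer that the call is the only contact in weeks 2 to 4. Section 4.3.3 calls for weekly blood pressure at the site. Footnotes a and c allow home readings and local laboratories, so site contact is possible but not assured.
- A reader might infer that the survey yields nothing. Footnote k's no-data statement covers only day 1 of cycle 1. The week 5 survey entry does not carry it, and the survey's recall period is in a separate document.
- A reader might infer that the sickest patients are missed. Hospitalisation of at least 24 hours and life-threatening events are SAEs whatever the attribution (7.2.3), and their reporting does not depend on the call.

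**Conclusion.** The concern holds in limited form. Table 7 conflicts with its own footnote on whether AE status in cycle 1 weeks 2, 3 and 4 is obtained from every patient or only from those who call. If footnote m is followed, symptomatic events are collected passively in those weeks. The consequence is a risk, not a demonstrated loss, and it is confined to non-serious transient symptoms and to their onset date and peak grade. Its size cannot be computed from the documents; the capture fractions above are assumptions. The primary endpoint and the Simon decision rule do not use these data and are unaffected. The change is worth making because it is cheap and serves a stated secondary objective.

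**What to change.** Replace footnote m with text to this effect: *In cycle 1 weeks 2, 3 and 4, study staff will contact every patient, by phone or at any site visit that week, ask about adverse events, and record the result on the eCRF, including no AE. Patients may also call at any time.* Align the AE and phone rows with it. In the same amendment, reconcile Section 4.3.3 with footnote a on where weekly blood pressure is taken, since this determines whether a site visit can serve as the contact; which wording is right is for the sponsor to decide.

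The cost is modest staff time for 36 to 93 short contacts in slots the schedule already marks, fewer where a site visit serves. It also takes a protocol amendment, with funder agreement and IRB review under Section 10.2, and possibly a small eCRF change for the no-AE entry. The recorded rate of low-grade AEs may rise slightly. A narrower alternative is to state that week 2 to 4 entries are required only from patients who call. That would remove the contradiction but leave collection passive.

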6.0 ENDPOINT ASSESSMENT

6.1 DEFINITIONS AND RESPONSE CRITERIA

Response and progression will be evaluated using the international criteria proposed by the Response Evaluation Criteria in Solid Tumors (RECIST) v 1.1 Committee. Changes in only the largest diameter (unidimensional measurement) of the tumor lesions are used in RECIST v 1.1.

Note: Lesions are either measurable or non-measurable using the criteria provided below. The term "evaluable" in reference to measurability will not be used because it does not provide additional meaning or accuracy.

6.1.1 Measurable and non-measurable disease

Measurable tumor lesions are defined as those that can be accurately measured in at least one dimension (longest diameter to be recorded) as ≥ 10 mm on CT (with less than 5 mm slice thickness) or ≥ 10 mm by caliper measurement during clinical examination. For superficial lesions measured by caliper, documentation by color photography including a ruler in the field of view is strongly recommended. MRI may be used in clinically appropriate circumstances to measure tumor lesions. Measurable lymph nodes are defined as those that can be accurately measured as ≥ 15 mm in short axis when assessed by CT.

Lesions failing to reach size criteria above and those that are not reproducibly measurable including leptomeningeal disease, effusions/ascites, inflammatory breast disease, diffuse lymphangitic disease and blastic bone lesions are defined as non-measurable. Previously irradiated lesions will also be considered non-measurable except if unequivocal progression is documented and radiation was greater than 28 days prior to study entry.

6.1.2 Target and non-target lesions

All measurable lesions up to a maximum of two lesions per organ and 5 lesions in total, representative of all involved organs, should be identified as **target lesions** and recorded and measured at baseline. Target lesions should be selected on the basis of their size (lesions with the longest diameter) and their suitability for accurate repeated measurements (either by imaging techniques or clinically). A sum of the diameter for all target lesions (long axis for tumor lesions and short axis for lymph nodes, if included) will be calculated and reported as the baseline sum diameters. The baseline sum diameters will be used as reference by which to characterize the objective tumor response.

All other lesions (or sites of disease) should be identified as **non-target lesions** and should also be recorded at baseline. Non-target lesions include measurable lesions that exceed the maximum numbers per organ or total of all involved organs as well as non-measurable lesions. Measurements of these lesions are not required but the presence or absence of each should be noted.

6.1.3 Guidelines for evaluation of response

Target lesion measurements should be obtained at baseline (within 4 weeks from initiation of regorafenib). Repeat measurements will be performed using the same technique as that used at baseline. For each measurement, a sum

of diameters will be calculated and non-target lesions will be followed as “present”, “absent” or in rare cases “unequivocal progression.”

6.1.3.1 Target lesion responses

Target lesions will be evaluated as follows:

- 6.1.3.1.1 **Complete response (CR):** Disappearance of all target lesions
- 6.1.3.1.2 **Partial response (PR):** $\geq 30\%$ decrease in the baseline sum diameters of target lesions
- 6.1.3.1.3 **Stable disease (SD):** Neither sufficient shrinkage to qualify for PR nor sufficient increase to qualify for PD, taking as reference the smallest sum diameters while on study
- 6.1.3.1.4 **Progressive disease (PD):** $\geq 20\%$ increase in the sum diameters of target lesions, taking as reference the smallest sum diameters while on study. The sum diameters must also demonstrate an absolute increase of 5 mm. The appearance of one or more new lesions also qualifies as PD.

6.1.3.2 Non-target lesions responses:

Non-target lesions will be evaluated as follows:

- 6.1.3.2.1 **Complete response (CR):** Disappearance of all non-target lesions with all lymph nodes < 10 mm in short axis.
- 6.1.3.2.2 **Non-CR/Non-PD:** Persistence of one or more non-target lesions
- 6.1.3.2.3 **Progressive disease (PD):** Unequivocal progression of non-target lesions (meriting discontinuation of regorafenib). The appearance of one or more new lesions also qualifies as PD.

6.1.4 Evaluation of best overall response

The best overall response is the best response recorded from the start of the treatment until the end of treatment taking into account requirements for confirmation. Please refer to Table 8 below.

Table 7: Evaluation of Best Overall Response

Target Lesions	Non-Target Lesions	New Lesions	Overall Response
CR	CR	No	CR
CR	Non-CR/non-PD	No	PR
CR	Not evaluated	No	PR
PR	Non-PD or not all evaluated	No	PR
SD	Non-PD or not all evaluated	No	SD
Not all evaluated	Non-PD	No	Inevaluable
PD	Any	Yes or no	PD
Any	PD	Yes or no	PD
Any	Any	Yes	PD

Patients with a global deterioration of health status requiring discontinuation of treatment without objective evidence of disease progression at that time

should be classified as having “symptomatic deterioration.” Every effort should be made to document the objective progression, even after discontinuation of treatment.

6.1.5 Confirmatory Measurement/Duration of Response

6.1.5.1 Confirmation

To be assigned a status of confirmed PR or CR, changes in tumor measurements must be confirmed by repeat assessment no less than 4 weeks after the criteria for response are first met. In the case of SD, follow-up measurements must have met the SD criteria at least once after study entry at a minimum interval of 8 weeks.

6.1.5.2 Duration of overall response/stable disease

The duration of overall response is measured from the time that measurement criteria are met for CR or PR (whichever is recorded first) until the first date that recurrent or progressive disease is objectively documented (taking as reference for progressive disease the smallest measurements recorded since treatment started).

The duration of overall CR is measured from the time that measurement criteria are first met for CR until the date that recurrent disease is objectively documented.

Stable disease is measured from the start of the treatment until the criteria for progression are met, taking as reference the smallest measurements recorded since treatment started.

6.2 PRIMARY ENDPOINT ASSESSMENT

The primary endpoint of the study will be progression-free survival (PFS) at 4 months, defined as the absence of progression at 4 months. Patients must complete at least 2 cycles of study treatment to be considered evaluable for this endpoint.

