Treatment Plan	Patients will be treated with regorafenib 160 mg PO daily for the first 3 weeks of each cycle (1 cycle = 4 weeks) until disease progression. Response evaluation will be every 2 cycles (approximately 2 months) using RECIST v 1.1.
Plan for statistical analysis	Optimal two-stage Simon design. First stage includes 12 patients. If > 3 patients have PFS > 4 months, and additional 19 will be enrolled for a total of 31 patients.

SCHEMA

[figure not shown]

TABLE OF CONTENTS

Synopsis	2
Schema	3
Table of Contents	4
List of Abbreviations	5
1.0 Introduction	6
2.0 Study Objectives	9
3.0 Selection of Subjects	9
4.0 Treatment Plan	12
5.0 Study Procedures	23
6.0 Endpoint Assessment	25
7.0 Adverse Events and Safety Monitoring	28
8.0 Drug Information	33
9.0 Statistical Methods and Determination of Sample Size	34
10.0 Study Management	35
Appendices	
References	40

LIST OF ABBREVIATIONS

ALT	Alanine aminotransferase
aPTT	Activated partial thromboplastin time
AST	Aspartate aminotransferase
BUN	Blood Urea Nitrogen
CR	Complete Response
CTCAE	Common Terminology Criteria for Adverse Events
ECOG	Eastern Cooperative Oncology Group
ERK	Extracellular Signal-regulated Kinases
FDA	Food and Drug Administration
FGFR	Fibroblast Growth Factor Receptor
GCP	Good Clinical Practice
GMP	Good Manufacturing Practice
HFSR	Hand-foot-skin reaction
IB	Investigator's Brochure
ICF	Informed Consent Form
ICH	International Conference on Harmonisation
IRB	Institutional Review Board
MAPK	Mitogen Activated Protein Kinase
PD	Progressive Disease
PDGFR- β	Platelet Derived Growth Factor Receptor-beta
PFS	Progression-free survival
PO	per oris , oral
PR	Partial Response
PS	Performance Status
PT/INR	Prothrombin time/ International Normalized Ratio
QD	quaque die , once daily
RAF	Rapidly Accelerated Fibrosarcoma
RAS	Rat sarcoma
RECIST	Response Evaluation Criteria for Solid Tumors
SAE	Serious Adverse Event
SD	Stable Disease
TK	Tyrosine Kinase
TTP	Time to Progression
VEGF	Vascular Endothelial Growth Factor
VEGFR	Vascular Endothelial Growth Factor Receptor

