4.0 TREATMENT PLAN

4.1 OVERVIEW

The eligible study population will consist of adult patients with histologically confirmed, measurable, unresectable or metastatic angiosarcoma who have progressive disease after prior treatment with ifosfamide, doxorubicin or a taxane. Patients will be treated with daily oral regorafenib (160 mg) for 3 weeks on followed by 1 week off (1 cycle = 4 weeks). Patients will continue treatment until disease progression or withdrawal due to unacceptable toxicity. Once off-treatment, patients will be followed for overall survival up to 5 years. An optimal two-stage Simon design will be employed. The first stage will include 12 patients. If > 3 patients achieve a PFS > 4 months, an additional 19 patients will be enrolled for a total of 31 patients.

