9.3 TRIAL DESIGN AND DETERMINATION OF SAMPLE SIZE

A two-stage optimal Simon design will be employed to test the null hypothesis that the probability of progression-free survival of 4 months or greater (P) is ≤ 0.22 versus the alternative that the probability ≥ 0.45 . To test this hypothesis with adequate power, a first stage involving 12 patients will be completed. If > 3 patients achieve progression-free survival of 4 months, the trial will be continued for a total of 31 patients. If > 11 out of 31 patients achieve progression-free survival of 4 months, the trial will reject the hypothesis that $P \leq 0.22$ and conclude that $P > 0.45$,

To determine sample size, the following parameters were employed: $P0 = 0.22$, $P1 = 0.45$, $\alpha = 0.05$ and $\beta = 0.20$. Computations originally performed using software PASS (www.ncss.com).

N1	R1	PET	N	R	Avg N	α	β	Satisfied
26	9	0.000	26	9	26.00	0.043	0.194	Single Stage
7	0	0.176	26	9	22.66	0.042	0.199	Minimax
12	3	0.739	31	10	16.96	0.047	0.188	Optimum

Definitions:

N1 – sample size in the first stage

R1 – drug rejection number in the first stage

PET – probability of early termination of study

N – combined sample size of both stages

R – combined drug rejection number after both stages

Avg N – average sample size if this design is repeated many times

α – probability of rejecting that $P < P0$ when this is true

β – probability of rejecting that $P > P1$ when this is true

P0 – response proportion P of a poor drug

P1 – response proportion P of a good drug

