9.4 PLANNED ANALYSES

Survival data will be analyzed using parametric (exponential) and non-parametric (Kaplan-Meier) methods. Exact methods for providing confidence intervals for proportions “surviving” landmarks will be used as needed. Statistical software will be SAS (and others as merited) and analysis will be conducted under the supervision of [name], in the Biostatistical Core Facility at Northwestern University.

Descriptive statistics (mean, standard deviation, mean change from baseline, etc.) will be presented for laboratory values. Detailed examination of AEs by NCI CTCAE grade and frequency tabulation will be presented. Missing data for partial dates on AEs or concomitant medications may be imputed.

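### Section 6.2 defines 4-month PFS without naming death, and no rule says how a patient without a 4-month assessment enters the Simon count

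*Combined protocol and SAP*

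**What the plan says.** **Primary endpoint.** Section 6.2 is the only place that defines it: "progression-free survival (PFS) at 4 months, defined as the absence of progression at 4 months". The next sentence of 6.2 limits evaluability to patients who complete at least 2 cycles.

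**PFS as a time.** Section 6.3, in the sentence on median PFS, has it "defined as the duration of time from start of treatment until time of progression or death, whichever occurs first".

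**Progression-free rate at 3 and 6 months.** Section 6.3 uses "the number of patients with progression absent at these timepoints divided by the total number of study patients". Death is again not named.

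**Decision rule.** The synopsis ("If > 3 patients have PFS > 4 months") and section 4.1 ("If > 3 patients achieve a PFS > 4 months") state the stage 1 rule in terms of PFS. Section 9.3 tests and counts PFS of 4 months without defining the term again. It requires more than 3 of 12 to continue. At the end, its text requires more than 11 of 31, while its design table gives a rejection number of 10, that is, more than 10.

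**Analysis.** Section 9.4 states: "Survival data will be analyzed using parametric (exponential) and non-parametric (Kaplan-Meier) methods". It adds "Exact methods for providing confidence intervals for proportions" that survive landmarks. Its only statement on missing data concerns partial dates of adverse events and concomitant medications.

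**Assessments.** Table 7 in section 5.0 schedules imaging after every 2 cycles (weeks 8, 16, 24), within 1 week either side, and a disease measurement at the end of treatment. After that, only survival calls about every 6 months are scheduled.

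**The concern.** There are two separate gaps.

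1. **Death.** The defining sentence of the primary endpoint leaves out an event that the usual meaning of PFS, and the plan's own definition in 6.3, includes. A patient who dies at month 3 with no recorded progression is a success by the letter of 6.2 and a failure by 6.3.
2. **Missing 4-month status.** A patient who completes 2 cycles and then stops for toxicity or symptomatic deterioration may have no scan near month 4. Section 6.1.4 asks for every effort to document progression after discontinuation but gives no scoring rule. Kaplan-Meier can censor such a patient. The Simon rule cannot, because it needs a yes or no for each of the 12 and the 31.

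The stake is the trial's only formal decision. The history of changes describes PFS at 4 months as the only endpoint with a pre-identified risk of error. When the count sits at a boundary, one patient changes the outcome. The 3- and 6-month rates have no stated test, so there only a reported rate is affected.

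**Working it through.** **Step 1. Reproduce the design.** Inputs from 9.3: P0 = 0.22, P1 = 0.45, stage 1 cut-off 3 of 12, total 31, final cut-off 10 (table) or 11 (text).

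P(reject | p) = Σ over x = 4 to 12 of Bin(x; 12, p) × P(Bin(19, p) ≥ r + 1 − x), with r = 10 or 11.

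| Quantity | Stated | Recomputed, > 10 | Recomputed, > 11 |
|---|---|---|---|
| Early termination at 0.22 | 0.739 | 0.7390 | 0.7390 |
| Average N | 16.96 | 12 + 0.261 × 19 = 16.96 | 16.96 |
| Type I error | 0.047 | 0.0468 | 0.0221 |
| Power at 0.45 | 1 − 0.188 = 0.812 | 0.8117 | 0.752 |

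The table reproduces with > 10. The disagreement between text and table is a separate matter that must be reconciled; both rules are carried below.

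**Step 2. Literal reading of 6.2.** Let d be the share of patients who complete 2 cycles and die before 4 months without documented progression. The documents do not give d. Under the literal reading the apparent success rate is p + d. Patients move only from failure to success, so the count can only rise. For illustration, d is set to an average of half or one patient in 31. The true progression-or-death rate is taken as 0.22, which is an assumption because the documents do not derive that figure.

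| Misscored on average | Apparent rate | Type I error, > 10 | Type I error, > 11 |
|---|---|---|---|
| 0 | 0.22 | 0.047 | 0.022 |
| 0.5 of 31 | 0.22 + 0.0161 = 0.2361 | 0.072 | 0.037 |
| 1 of 31 | 0.22 + 0.0323 = 0.2523 | 0.106 | 0.058 |

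**Step 3. Stage 1 boundary.** P(exactly 3 true successes of 12) at 0.22 is 0.250. This is only the chance of sitting at the boundary. A wrong continuation also needs at least one misscored patient among the other 9, each misscored with probability d/0.78:

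- d = 0.5/31: 0.250 × [1 − (1 − 0.0207)^9] = 0.250 × 0.171 = 0.043.
- d = 1/31: 0.250 × [1 − (1 − 0.0414)^9] = 0.250 × 0.316 = 0.079.

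**Step 4. Missing 4-month status.** The share m is not in the documents; 5% and 10% are assumed, missing independently of outcome, with rule > 10. Scored as not a success, the rate is p(1 − m). Scored as a success, it is p(1 − m) + m.

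| m | Not a success: power at 0.45 | Not a success: type I | Success: type I |
|---|---|---|---|
| 0 | 0.812 | 0.047 | 0.047 |
| 5% | 0.749 (rate 0.4275) | 0.034 | 0.122 (rate 0.259) |
| 10% | 0.675 (rate 0.405) | 0.023 | 0.245 (rate 0.298) |

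The unwritten choice therefore affects both error rates.

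**Step 5. Which assessment is month 4?** Week 16 is day 112, with a window of days 105 to 119. Four calendar months is 4 × 30.44 ≈ 122 days, and the next scheduled scan is week 24 (day 168). If calendar months are meant, no scheduled window contains the date. If 0.22 refers to day 122 and PFS is exponential (assumed), the null rate at day 112 is 0.22^(112/121.75) = 0.248. The time point and the null must therefore be set together.

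**The case against.** The strongest reply is that this is loose wording. Every statement of the primary endpoint uses the word survival. The history of changes shows the primary objective moving from PFS to PFS at 4 months, which suggests the same quantity read at a landmark. Section 9.4 also speaks of proportions surviving landmarks. That stands as evidence of intent. It does not remove the problem, because 6.2 supplies its own definition instead of relying on the usual one.

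It is also fair that the exposed group is narrow. It needs 2 completed cycles, no progression at week 8, and death before month 4 with progression never documented. Eligibility requires ECOG 0 or 1 and life expectancy of at least 4 months, and the introduction attributes nearly all deaths to metastatic disease. This limits the size of the first gap. It does not bear on the second.

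A reader might infer stronger conclusions that the documents do not support:

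- That 9.3 directly contradicts 6.2. It never names death; the link runs only through the term PFS as defined in 6.3.
- That the 3- and 6-month rates contradict the PFS definition. They are a separately named endpoint with the same omission.
- That there is a 25% chance of a wrong stage 1 decision. As step 3 shows, 0.250 is only the chance of being at the boundary.

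**Conclusion.** The point holds as a defect in the definition of the primary endpoint, with a likely intended reading. Section 6.2 as written permits a death to score as a success, and no section scores a patient with 2 or more cycles and no 4-month assessment. The first gap can only push the Simon count upward.

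The size cannot be taken from the documents. An average of half to one misscored patient in 31 gives type I error of 0.072–0.106 (> 10) or 0.037–0.058 (> 11). The chance of a wrong continuation from exactly 3 of 12 is about 0.04–0.08. These figures assume that 0.22 is a progression-or-death rate and that patients are independent. They show sensitivity and do not predict the trial's actual error rate. Confidence is high that the two gaps exist and lower on how often they would matter. This should be fixed before the count is made.

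**What to change.** In 6.2:

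- Define success as alive and without RECIST progression at 4 months.
- Count death from any cause before 4 months as failure.
- Amend the 2-cycle evaluability sentence so that it does not remove such deaths from the primary count. Otherwise a death at week 5 would be both a failure and not evaluable.
- Count a patient with no assessment showing freedom from progression at the 4-month time point, or later, as not a success.
- Have the biostatistician state which assessment is the 4-month time point, consistent with the basis of the 0.22 null.

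In 6.3, apply the same death rule to the 3- and 6-month rates. In reporting, give the Kaplan-Meier 4-month PFS, with progression or death as the event, beside the primary rate. Section 9.4 already plans that method.

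**Cost.** A few sentences. If week 16 is confirmed as the time point, no scan or visit is added; if a calendar date is chosen, the imaging schedule needs checking against it. The reported rate will be lower than under the literal reading and may differ a little from the Kaplan-Meier estimate, which censors unknown status. Power falls if scans are missing: from 0.812 to 0.749 at 5% or 0.675 at 10% (assumed shares, rule > 10). Obtaining the 4-month assessment in patients who stop early would limit that loss.
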